The study subjects were male and female adults, enrolled at the Physical Therapy Department of the Physical Medicine and Rehabilitation Hospital in Kuwait City. Participants were included if they fulfilled the following criteria: 1) diagnosed of plantar heel pain in accordance with the Clinical Guidelines linked to the International Classification of Function, Disability and Health from the Orthopedic Section of the American Physical Therapy Association;²³⁸⁹ 2) aged 21 to 60 years at admission to the study, according to the Kuwaiti Ethical Committee; 3) a history of PHP for over one month, showing no improvements with previous conservative treatment; 4) the ability to walk 50 meters without any support; 5) the presence of MTrPs on plantar and calf muscles based on an initial physical examination carried out by a physiotherapist (MA) with experience and training in MTrPs; 6) accepting treatment from a male physiotherapist; 7) the ability to understand the study and the informed consent, as well as having signed the consent form.

The exclusion criteria were: 1) needle phobia; 2) needle allergy or hypersensitivity to metals; 3) the presence of coagulopathy or use of anticoagulants according to medical criteria; 4) the presence of peripheral arterial vascular disease; 5) pregnancy; 6) dermatological disease affecting the dry needling area; 7) the presence of any chronic medical condition which might preclude participation in the study, such as: malignancy, systemic inflammatory disorders (e.g., rheumatoid arthritis, psoriatic arthritis, ankylosing spondylitis, septic arthritis), neurological diseases, polyneuropathy, mononeuropathy, and sciatica; 8) treatment of plantar heel pain with needling or acupuncture during the last four weeks; 9) history of injection therapy in the heel over the previous three months; and 10) previous history of foot surgery or fracture. Receiving or implementing any form of treatment for the plantar heel pain (taping, night splints, massage therapy or footwear modifications) during the trial was considered withdrawal criteria.

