specific self-stretching for the plantar fascia.¹⁹ The frequency of calf and plantar fascia-specific self-stretching exercises was twice a day, using intermittent stretching lasting 20 seconds, followed by 20-second rest periods, for a total of three minutes per stretch.¹¹ Compliance with the selfstretching protocol was registered before each treatment session and at the four-week follow-up. The muscles considered for invasive physical therapy treatment were the soleus, gastrocnemius, quadratus plantae, flexor digitorum brevis and abductor hallucis. These muscles typically refer pain to the heel and are muscles than can be directly palpated or that can be needled precisely and safely without ultrasound guidance. The clinician performed a physical exam to find MTrPs following the criteria by Travell and Simons: 1) the presence of a taut band and 2) identification of an exquisite spot tenderness or a nodule.⁷ A flat palpation or pincer palpation technique was used to palpate the MTrPs, depending on the muscle being assessed. If a muscle contained more than one MTrP, the most sensitive MTrP was treated, according to the patient's perceived pain upon palpation. If the patient presented bilateral pain, the clinician treated both sides. The patient's position (supine, prone or lateral decubitus position) depended on each muscle examined and was the same for the assessment as well as for the intervention.

Each participant received four individual physical therapy sessions, once a week. Participants was treated by one physical therapist registered at the Kuwait Ministry of Health (ZA) with five years of practical experience in the field of dry needling and appropriate training in the protocol. The duration of each session was approximately 30 minutes.

Participants were instructed to use the appropriate dose of medication as prescribed by their Physical Medicine and Rehabilitation physician (analgesics and non-steroidal anti-inflammatory medications) and were required to report any changes to the assessor during the evaluations if they took any additional medication or underwent any treatment during the intervention.

Invasive Intervention Groups: Dry Needling and Percutaneous Needle Electrolysis

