Specific needles for dry needling were used during invasive treatments (Agu-punt, Spain). Needle length was determined by the location of the MTrP and ranged from 30 to 75mm in length (or longer if necessary, according to the patients' characteristics). The diameter of the needle was 0.25-0.30 mm. If the participant was sensitive to the needle insertion, the level of manipulation was reduced. If this measure proved insufficient for reducing the painful stimulus, needle manipulation ceased altogether and the needle was left in situ.^{21 22}

To maintain appropriate hygienic conditions during the invasive treatments, the clinician wore latex gloves and thoroughly cleaned the skin of the area to be needled with an antiseptic solution (70% Propan-2-ol, Skin-des). Upon removal of the needle, the area was firmly compressed for 10 seconds. The needle was discarded after each single use. In both groups, the intervention was terminated in the case of severe adverse effects and if the participant did not wish to continue.

Dry Needling Arm

Once the clinician located the MTrP, the needle was inserted over the same and a rapid needle entry was performed. The chosen technique for manipulating the needle was the technique described by Hong, which consists of a rapid needle entry and exit (fast in/fast out), in order to obtain a local twitch response, lasting 5 seconds employing a rhythmic movement at approximately 1Hz/sec (5 entries).

Percutaneous Needle Electrolysis Arm

The electrotherapy equipment used (Physio Invasiva, PRIM Fisioterapia, Spain) produced a

continuous galvanic current through the cathode while the patient held a hand-held anode. ¹⁸ Once the needle reached the relevant treatment area, this was needled in exactly the same manner as in the dry needling group, with the only difference being that the needle was transmitting an electrical current with an intensity of 1.5 mA (intensity was adapted to patient's characteristics according to their pain tolerance).

Study Variables

An independent assessor (MA) blinded to treatment group allocation conducted all assessments at baseline, and at the 4, 8, 12, 26 and 52-week follow-up. Demographic and disease data were collected at baseline.

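### Latex gloves are specified for needling in both arms with no non-latex alternative, and no exclusion names latex allergy; non-latex gloves would be a small, cheap safety gain

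*Combined protocol and SAP*

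**What the plan says.** The hygiene paragraph under Invasive Intervention Groups: Dry Needling and Percutaneous Needle Electrolysis applies to both arms. It states that "the clinician wore latex gloves and thoroughly cleaned the skin of the area to be needled with an antiseptic solution". It adds: "Upon removal of the needle, the area was firmly compressed for 10 seconds". No other glove material is mentioned anywhere in the document.

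Under Participants, exclusion criterion 2 is "needle allergy or hypersensitivity to metals". It is the only criterion about allergy to a material. Criterion 6 concerns skin disease at the needling site, which is a different matter. Criterion 7 excludes "any chronic medical condition which might preclude participation in the study" and then gives examples. The examples are not exhaustive, and none of them is an allergy.

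The extent of exposure follows from Procedure and interventions:

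- "The muscles considered for invasive physical therapy treatment were the soleus, gastrocnemius, quadratus plantae, flexor digitorum brevis and abductor hallucis"
- "If a muscle contained more than one MTrP, the most sensitive MTrP was treated"
- "If the patient presented bilateral pain, the clinician treated both sides"
- "Each participant received four individual physical therapy sessions, once a week"

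The hygiene paragraph also provides for stopping the intervention if severe adverse effects occur and the participant does not want to go on.

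**The concern.** Criterion 2 shows that the investigators treated hypersensitivity to a contact material as a reason to keep someone out of the trial. Latex is another material that the plan itself brings to skin being punctured, yet it has neither a named exclusion nor a substitute.

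The remaining safeguards are partial. Criterion 7 works only if the allergy is known, is disclosed, and is judged to preclude participation. Stopping for severe adverse effects acts after a reaction has happened. A participant's own wish to stop protects beforehand only someone who already knows of the allergy. Routine clinical screening may have filled the gap, but the document does not describe it.

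What is at stake is an avoidable exposure for a latex-allergic participant, repeated weekly. The validity of the trial is not at stake, because both arms are treated alike.

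**Working it through.** The plan gives no figure on this point, so there is none to reproduce. The check has two parts: a reading of the text, and a count of how often the exposure can occur.

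**Reading of the text**

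| Question | What the document shows |
|---|---|
| Glove material | Latex, in the paragraph shared by both arms |
| Alternative material | None stated |
| Latex allergy named as an exclusion | No; criterion 2 covers needles and metals only |
| Another exclusion that could apply | Criterion 7, by clinician judgement |
| Latex screening described | No |
| Action if a reaction occurs | Stopping for severe adverse effects, which is reactive |

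**Count of exposures**

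Inputs from Procedure and interventions: 5 listed muscles (gastrocnemius counted once, as the list does), 1 trigger point treated per muscle, 1 side or 2, and 4 sessions. From the hygiene paragraph: 10 seconds of compression per site. From the sample-size paragraph under Participants: 102 participants in total.

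Maximum sites per session = muscles × trigger points per muscle × sides:

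- One side: 5 × 1 × 1 = 5
- Both sides: 5 × 1 × 2 = 10

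Maximum sites per participant = sites per session × sessions:

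- One side: 5 × 4 = 20
- Both sides: 10 × 4 = 40

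Maximum compression time per participant = sites × 10 s:

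- One side: 20 × 10 = 200 s
- Both sides: 40 × 10 = 400 s

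Maximum sessions needing gloves = 102 × 4 = 408.

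These are ceilings. A participant has fewer sites if some of the five muscles have no trigger point. The seconds refer to the compression step alone. The text does not say whether compression was by gloved hand or through a dressing, so they are an upper limit on glove contact in that step. They do not cover contact during cleaning or needling, and they do not measure harm.

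The expected number of latex-allergic participants would need a prevalence, and the number of reactions a reaction rate. The document gives neither, so neither number is calculated. The finding rests on the wording of the plan and needs no rate.

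**The case against.** The strongest case against is that the point is true but trivial.

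- **No measured hazard.** The document does not mention latex allergy and gives no prevalence or reaction count. The site and second counts describe a procedure, not a harm. This stands, and it is why no harm is quantified. It limits the size of the point but does not alter what the plan specifies.
- **Too late to act.** The document is dated 23-1-2021 and describes recruitment, treatment and assessment in the past tense. Nothing in it indicates that any session remains to be given. This also stands. The benefit is confined to reuse of the protocol, unless some sessions were in fact still outstanding.
- **Safeguards may lie elsewhere.** The Design section says the protocol was published separately, and participants received standardized oral and written information before consenting. Neither source is available here, so a latex question or warning could exist in either. That is possible and cannot be excluded. A non-latex glove would still remove the exposure without depending on such a question.
- **Partial cover already exists.** Criterion 7 could exclude a known latex allergy, and a participant can stop. This is correct. The gap is mainly for people whose allergy is unknown, undeclared or not judged to fall under criterion 7.
- **Selective.** The antiseptic is not named in the allergy screening either. That is so. The gloves are singled out because a change of material removes this exposure outright, with no reliance on screening.
- **No scientific effect.** Agreed. The case for the change is participant safety alone.

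**Conclusion.** The point holds as a minor safety improvement, to be considered rather than required. The plan specifies latex gloves in both arms, gives no alternative, and names only needles and metals among material allergies. A latex-allergic participant is protected beforehand only through clinician judgement under criterion 7, through the participant's own knowledge of the allergy, or through practice that the document does not describe.

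The exposure is bounded at 20 needled sites per participant for one-sided pain or 40 for bilateral pain. This assumes that every listed muscle is treated at every session. The number of people affected is unknown. There is no effect on bias, power, randomization or analysis. Confidence is medium, because screening may be described in material outside this document. The point ranks below anything that bears on the trial's validity.

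**What to change.** In the hygiene paragraph, specify non-latex gloves in place of latex gloves for both arms. Leave the eligibility criteria as they are. Changing the glove is preferable to adding a latex exclusion because no otherwise eligible person is lost.

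The cost is a change of glove supply for at most 408 sessions if the protocol were run again at the same size. The document gives no glove price, so calling this cheap is a judgement. The target of 102, the randomization, the blinding and the analysis do not change. If non-latex gloves or latex screening were already used in practice, one sentence saying so would settle the point.

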treatment that consists of the application of a galvanic electrolytic current that causes a controlled local inflammatory process in the target tissue. This promotes phagocytosis and the subsequent regeneration of the affected tissue. ¹⁶ ¹⁷ Currently, percutaneous needle electrolysis is being used in clinical practice to manage MTrPs, however, there are no studies supporting any additional beneficial effects of the same over dry needling.

From a biological point of view, it seems reasonable to hypothesize that subjects may display improvements thanks to the mechanical effects of the needle, and that patients may experience superior benefits when the electrolysis effect is added to the mechanical stimulus provided by the needle. Therefore, the aim of this RCT was to compare the effectiveness of dry needling versus percutaneous needle electrolysis for improving the level of pain, function and quality of life of patients suffering from PHP caused by MTrPs.

METHODS

Design

This study was a prospective, parallel-group RCT with blinded outcome assessment. Participants were recruited from Kuwait City, Kuwait, and both the assessment and intervention were conducted at the Physical Medicine and Rehabilitation Hospital in Kuwait. The study was conducted in compliance with the Helsinki Declaration of Human Rights and ethical approval was obtained by the Medical Ethics Committee of the State of Kuwait Ministry of Health, with reference number 642/2017. The study protocol has been previously published¹⁹ and the trial is registered at Clinicaltrials.com, number NCT03236779. This RCT was reported in accordance with the CONSORT statement for non-pharmacological trials.

Participants

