The primary outcome was the Foot Pain domain of the Foot Health Status Questionnaire (FHSQ), a validated measure of foot-health status²³ that has been used in similar trials, which evaluated the effectiveness of different interventions for plantar heel pain. ⁸ ²⁴ ²⁵ Individual item scores were inserted into a computer program (FHSQ V.1.03) which, after data transformation, provides a score ranging from 0 to 100 for each domain, ²⁶ with greater scores reflecting a better condition. ²⁷ Secondary outcomes were the Foot Function, Footwear and General Foot Health domains of the Foot Health Status Questionnaire, as well as the average and maximum level of pain over the past 48 hours using the visual analogue scale (VAS). Participants were explained that a score of 0 indicated the absence of pain whereas a score of 10 represented the maximum tolerable pain. Additionally, before each treatment session, they were asked to complete the VAS and after each treatment session, participants were asked to score their current pain immediately upon standing up and walking a few steps. The VAS is widely used and is both valid and reliable. ²⁸⁻³⁰

Quality of Life (QoL) was assessed with the EQ-5D-5L, which was completed by the participants at baseline and at the 4, 8, 12, 26 and 52-week assessments. The EQ-5D-5L self-report questionnaire is a descriptive system with five questions, each representing one dimension of Health-related Quality of Life, i.e. mobility, self-care, daily activities, pain/discomfort and depression/anxiety. Each dimension can be rated on five levels: no problems, slight problems, moderate problems, severe problems and extreme problems. Together, the results serve to classify people into 1 of 3125 possible health states.³¹ These health states are subsequently transformed to quality of life values with the EQ-5D-5L crosswalk value sets.³²

Statistical Analysis

The statistical analysis was performed using IBM SPSS Statistics (version 25, IBM, Chicago, IL) by intention to treat, with the last observation carried forward. The investigator who performed the analyses was masked to group allocation. The significance level for all statistical tests was set at $P \le 0.05$.

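### The device and hand-held anode are described for the electrolysis arm only, with no participant masking, while every efficacy outcome is rated by the participant: high risk of bias of unknown size and direction

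*Combined protocol and SAP*

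**What the plan says.** The closing part of the background sets the question: does electrolysis add benefit over the mechanical effect of the needle?

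- **Electrolysis.** The section on the Percutaneous Needle Electrolysis Arm describes equipment delivering a "continuous galvanic current through the cathode while the patient held a hand-held anode". The nominal intensity is 1.5 mA, and "intensity was adapted to patient's characteristics according to their pain tolerance". The tissue is needled as in the other arm, "with the only difference being that the needle was transmitting an electrical current".
- **Dry needling.** The section on the Dry Needling Arm describes the needle alone: "Once the clinician located the MTrP, the needle was inserted over the same and a rapid needle entry was performed". It mentions no equipment, electrode or inactive current.
- **Blinding.** Design calls the trial a "prospective, parallel-group RCT with blinded outcome assessment". Study Variables describes an independent assessor "blinded to treatment group allocation conducted all assessments at baseline" and at each follow-up. Statistical Analysis adds: "The investigator who performed the analyses was masked to group allocation". Masking of participants is not mentioned, and no check of what participants believed is planned.
- **Outcomes.** "The primary outcome was the Foot Pain domain of the Foot Health Status Questionnaire (FHSQ"). The secondary outcomes are the other FHSQ domains, VAS pain (48-hour average and maximum, plus ratings around each session) and the EQ-5D-5L.

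**The concern.** As described, the arms differ in more than the current. One arm also has visible equipment, an electrode in the hand and an intensity adjusted to what the participant tolerates, at each of four weekly sessions. These are cues to allocation.

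Blinding the assessor protects an outcome that the assessor judges. Here the participant supplies every score, so the blinded person collects ratings from someone who may know the arm. Blinding the analyst protects analysis decisions but not the data.

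At stake is the trial's only between-arm comparison. A shift in ratings caused by knowing the arm enters the estimate in the same way as an effect of the current. Baseline adjustment, mixed models and Bonferroni correction cannot separate the two. Nor can a larger sample, because the shift stays while the standard error shrinks.

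**Working it through.** **1. Cues and protection, element by element**

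| Element | Electrolysis | Dry needling |
|---|---|---|
| Needling technique | Same | Same |
| Electrotherapy device | Described | None described |
| Electrode held by participant | Described | None described |
| Current | 1.5 mA, adapted to tolerance | None described |
| Participant masked | Not stated | Not stated |
| Assessor and analyst blinded | Stated | Stated |
| Who rates FHSQ, VAS, EQ-5D-5L | Participant | Participant |

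The persons stated to be blinded are not the persons who produce the scores.

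**2. The plan's own figure**

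Inputs, from the sample-size paragraph under Participants: difference 13 points, SD 20, power 80%, alpha 0.05 (sidedness not stated; two-sided assumed).

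- Normal approximation: n = 2 × (1.960 + 0.842)² × 20² / 13² = 37.2, so 38 per group.
- t-test solution: 38.14, so 39 per group, with power 0.81 at 39.

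The stated 39 per group is reproduced, so SD 20 and the t-test are a fair basis for step 3.

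**3. What a rating shift would do (illustration)**

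The documents give no figure for the effect of knowing the arm. I assume a shift b of 2 to 5 points (2/20 = 0.10 SD to 5/20 = 0.25 SD) towards one arm, with no true effect.

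- SE = 20 × √(2/n). With n = 39 this is 4.53. With n = 51 (102/2) it is 3.96.
- The chance of falsely favouring that arm is P(T > critical value), where T is noncentral t with 2n − 2 degrees of freedom and noncentrality b/SE. For example, b = 5 and n = 39 gives 5/4.53 = 1.10.

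One unadjusted two-sided test at 0.05:

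| Shift b (points) | 39 per arm | 51 per arm |
|---|---|---|
| 0 | 2.5% | 2.5% |
| 2 | 6.4% | 7.2% |
| 3 | 9.6% | 11.3% |
| 4 | 13.8% | 16.9% |
| 5 | 19.2% | 23.9% |

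The rates are higher at 51 per arm, which shows that sample size does not help.

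**4. With the Bonferroni correction**

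Statistical Analysis applies Bonferroni to between-group differences at time points but does not say over how many comparisons. If it spans the five follow-ups (4, 8, 12, 26 and 52 weeks), each is tested at 0.05/5 = 0.01. The base chance per time point is then 0.5%. For shifts of 2 to 5 points it rises to 1.6-6.7% with 39 per arm and 1.9-9.1% with 51. The chance of at least one false finding across the five visits would be higher than the rate at a single visit.

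**The case against.** **The plan never claims that participants were masked.** This is correct. It claims a blinded assessor and a masked analyst, so this is a design weakness and not a contradiction. A reader might also take the only-difference sentence as a false claim that the arms matched in everything but current. In context it describes how the tissue was needled, and it says nothing about the surroundings.

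**Not every participant need know their arm.** A reader might infer that all participants can tell. The documents do not support that. Those who hold the anode and feel the current have a direct cue. For dry needling it depends on what the standardized information under Randomization said about the other arm, and this is not reported. Someone never told of an electrode learns nothing from its absence. A dummy electrode is also absent only in the sense that none is described.

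**The direction is unknown.** A reader might infer that expectation of a device-based treatment favours electrolysis. Nothing in the documents reports participants' preferences. Both arms receive active needling, the same planned sessions and the same stretching. Current set by pain tolerance could also worsen ratings through discomfort.

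**The calculation is not the planned test.** The plan uses baseline-adjusted mixed models with Bonferroni. The correction could lower the per-visit rates, as step 4 shows, while baseline adjustment could raise them. A constant shift out to 52 weeks, after four weekly sessions, is a further simplification. The figures therefore show scale only.

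**Current may be felt, so masking would fail anyway.** This limits what masking can achieve. It does not justify leaving the visible cue in one arm only.

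**It may be too late.** The document is dated January 2021 and is in the past tense. If treatment is complete, only the reporting changes remain.

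**Conclusion.** The point holds as a high risk of bias. The device and anode are described for one arm only, no participant masking is described, and all efficacy outcomes are self-rated. The stated blinding of assessor and analyst leaves that risk in place for the trial's central comparison.

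Size and direction cannot be derived from the documents. The 6-19% (39 per arm) and 7-24% (51 per arm), or about 2-7% and 2-9% per time point at 0.01, rest on four assumptions: a shift of 2 to 5 points, no true effect, SD 20, and one unadjusted t-test. They should not be read as this trial's actual error rates, nor as evidence that bias occurred or that it favoured electrolysis.

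**What to change.** **For participants not yet treated**

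- Set up the same device in both arms, and have dry-needling participants hold the same electrode with no current delivered.
- Do not disclose the arm, and word the consent form so that this is permitted.
- After the fourth session, ask each participant to guess their arm, and report the guesses by arm.

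Cost: a few minutes of set-up per session with equipment the trial already uses, and one question. No extra staff are needed. Downside: the current can be felt, so masking would be only partial; the guesses show how partial.

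**Whether or not treatment is complete**

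- Replace the blinding phrase under Design with: blinded assessor and analyst; participant-reported outcomes, participants not masked (or partially masked, if the dummy electrode is used).
- State the limitation, and limit the conclusion so that a difference between arms is not attributed to the current alone.

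These are text changes and cost almost nothing.
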